### 1.2 Transdifferentiation is an Adaptive Response to Long-term ADT

There is marked heterogeneity across mCRPC patients with widely varying clinical outcomes and therapeutic responses driven largely from diverse mechanisms of resistance to overcome androgen-signaling inhibition. Transdifferentiation to a neuroendocrine phenotype, termed treatment-emergent small cell neuroendocrine prostate cancer (t-SCNC), represents a highly aggressive and lethal subset of prostate cancer that is becoming increasingly common in previously treated mCRPC. While *de novo* SCNC represent 1-2% of new cases, in our prospective, multi-institutional study of over 200 unselected mCRPC patients previously treated with ARPI, treatment-emergent SCNC (t-SCNC) was identified in 17% of mCRPC biopsies (Aggarwal et al., 2018). Compared to mCRPC with adenocarcinoma features, t-SCNC is characterized by decreased AR signaling, enrichment for loss of *RB1* and *TP53*, and enrichment of activation of transcriptional factors including *EZH2*, *POU3F2*, *ASCL1*, among others.

It is hypothesized that t-SCNC arise clonally from adenocarcinoma, though through which molecular mechanisms, i.e. de-differentiation to a primitive progenitor or transdifferentiation from epithelial to neuronal phenotypes, remains under active investigation (Aggarwal et al., 2019; Beltran et al., 2016; Guo et al., 2011; Zou et al., 2017). Importantly, patients with t-SCNC exhibit poor prognoses compared to mCRPC with adenocarcinoma (Aggarwal et al., 2018; Small et al., 2016). Furthermore, patients with t-SCNC have limited effective treatment options outside of traditional platinum-based chemotherapies, which itself have limited durability of response and carry significant risk of undesired side effects (Aparicio et al., 2013). In the Aparicio et al. study, 97% of patients treated with platinum therapy experienced progression of disease with a median time of 3.0 months. Therefore, there is an unmet clinical need to develop new, durable therapies for these two high-risk mCRPC subtypes.

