### **3.5 Criteria for Treatment Discontinuation**

In the absence of treatment delays due to AEs, treatment (both study drugs) may continue until first occurrence of one or more of the following:

- Radiographic PD by PCWG3/RECIST 1.1 criteria. If patients are clinically stable in the judgment of treating investigator, continuation of protocol therapy is allowed until progression is confirmed by repeat tumor assessment performed  $\geq 4$  weeks following first scan demonstrating progression.
- Unequivocal clinical progression
- Inter-current illness that prevents further administration of treatment;
- Unacceptable AE(s);
- Participant decides to withdraw from the study;
- Significant participant non-compliance with protocol;
- Receipt of non-protocol therapy
- General or specific changes in the participant's condition render the participant unacceptable for further treatment in the judgment of the investigator
- Study closure
- Completion of 2 years of protocol therapy.

Patients with PSA-only progression in the absence of radiographic or unequivocal progression should remain on study treatment per PCWG3 guidelines.

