 Including complete blood cell (CBC) with differential and platelet count. All laboratory assessments have a window of +/- 3 days.

 Chemistry panel includes: sodium, potassium, chloride, bicarbonate, blood urea nitrogen (BUN)/creatinine, calcium, alkaline phosphatase (ALP), ALT/AST, total bilirubin. All laboratory assessments have a window of +/- 3 days.

 Thyroid function tests - including thyroid-stimulating hormone (TSH), with reflex free T4, total/free T3. Thyroid function tests will be performed on Day 1 of each Treatment Cycle.

 Whole Blood for peripheral immune marker assessment will be collected on C1D1 (pre-dose), C2D1 (pre-dose), C3D1 (pre-dose), and End of Treatment.

 Tumor assessment will be performed with CT Chest/Abdomen/Pelvis and whole-body bone scan during screening, C4D1 (-14d), C7D1 (-14d) and on D1 (-14d) of every 4 cycles thereafter (e.g. C11D1, C15D1). If PD by RECIST1.1/PCWG3, confirmatory scans are required ≥ 4 weeks following first scan showing progression. Lesions on chest x-ray are acceptable as measurable lesions when they are clearly defined and surrounded by aerated lung. However, CT is preferable.

 CT with contrast or MR brain is required during Screening only if history of brain metastases or clinical suspicion.

 Optional Tumor biopsy will be performed during Screening. Biopsy only required if no biopsy has previously been done. If no metastatic lesion is safely accessible to tumor biopsy, this requirement will be waived. Bone or soft tissue lesion is allowed, but soft tissue will be prioritized. If a patient has archival tissue obtained within 90 days of C1D1, and no intervening therapy between tissue acquisition and C1D1, the requirement for fresh tumor biopsy will be waived. Tumor biopsy at progression is

optional and should be the same lesion as Screening biopsy whenever feasible. Biopsy at PD also optional. Refer to Lab Manual for detail regarding tissue collection/biopsy.

 If a subject experiences a treatment-emergent rash of Grade  $\geq 2$ , consider referral to Dermatology for skin biopsy if clinically indicated per conventional (standard of care) rash management. See Section 5.4 for rash management.

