### 8.3.3 Secondary Analysis (or Analysis of Secondary Endpoints)

Secondary Objective 1 Analysis: AEs will be recorded and severity-graded using CTCAE version 5.0. Clinically significant laboratory, physical exam, scan, and ECG abnormalities will be captured as AEs. The frequency and severity of AEs will be descriptively reported on a per-patient analysis.

Secondary Objective 2 Analysis: The median radiographic progression-free survival determined by PCWG3 criteria

Secondary Objective 3 Analysis: PSA50 and PSA90 response are defined as above, a  $\geq 50\%$  and  $> 90\%$  decline from baseline in serum PSA, respectively, confirmed by repeat measurement  $\geq 4$  weeks later. The PSA50 and PSA 90 response proportions will be reported along with 95% confidence interval for each study cohort, for the subset of PSA-evaluable patients (serum PSA  $\geq 2$  ng/mL at baseline).

Secondary Objective 4 Analysis: Median progression-free survival will be determined for each cohort as from the date of first dose of protocol-defined therapy, using Kaplan-Meier product limit method. Progression is defined as per Section 7.1.4. The first scan time point demonstrating radiographic progression requires confirmatory scans performed  $\geq 4$  weeks after first scan time point to confirm progression. Patients who discontinue treatment for reasons other than those listed above (e.g. AE, patient withdrawal) will be censored by the date of last treatment.

Secondary Objective 5 Analysis: The median overall survival along with 95% confidence interval will be determined from the date of first dose of protocol-defined therapy until death from any cause, using the Kaplan-Meier product limit method. Patients will be followed for long-term survival as outlined in the Study Procedures. Patients who withdraw from study will be censored for analysis of overall survival using the date of study withdrawal.

Secondary Objective 6 Analysis: The objective response rate and median duration of response will be reported along with 95% confidence interval, for the subset of patients with measurable soft tissue disease by RECIST 1.1 criteria.

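### Radiographic progression must be confirmed by a second scan, but no rule covers a progression that is never confirmed, so rPFS may be overstated

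*Combined protocol and SAP*

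**What the plan says.** - **Confirmation.** Section 8.3.3, under Secondary Objective 4: "The first scan time point demonstrating radiographic progression requires confirmatory scans performed" at least 4 weeks after it. The sentence before reads "Progression is defined as per Section 7.1.4".
- **Censoring.** The same paragraph: "Patients who discontinue treatment for reasons other than those listed above (e.g. AE, patient withdrawal) will be censored by the date of last treatment".
- **Staying on treatment.** Section 3.5: "If patients are clinically stable in the judgment of treating investigator, continuation of protocol therapy is allowed until progression is confirmed" by a repeat assessment. It makes no such provision for patients who are not stable.
- **Imaging.** The Section 6.1 calendar marks CT and bone scan under Screening and Cycle 2+ only. Sections 6.3.3 to 6.3.5 list no imaging at End of Treatment or at the 30-day and 100-day visits, and Section 6.3.6 follows survival by chart or telephone. Footnote 6 to the calendar nevertheless says "If PD by RECIST1.1/PCWG3, confirmatory scans are required" at least 4 weeks later.
- **Events.** Section 2.3 defines the rPFS event (Secondary Objective 2) as radiographic progression by PCWG3 or death. Section 7.1.4 has a wider composite definition of progression. It includes global deterioration that forces discontinuation, and an indication for radiotherapy or for other systemic therapy.
- **Bone lesions.** Section 7.1.4 asks for confirmation at 6 weeks or more after the first reassessment. For later scans it states no confirmation and dates progression at the first scan.
- **Rule for rPFS.** Section 8.3.1 promises censoring criteria for each endpoint in 8.3.3. Secondary Objective 2 gets one line there, with neither an event rule nor a censoring rule.

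**The concern.** Whether a confirming scan exists depends on prognosis. A stable patient can wait for it on treatment. A deteriorating patient is likely to stop at the first progressing scan, after which no scheduled visit contains a scan. If progression counts only once confirmed, the missing confirmations fall mostly among patients doing badly. Censoring them would be informative and would push the Kaplan-Meier curve upward. Counting them only at death would delay their events.

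The censoring date adds a second problem. A patient who stops for another reason is censored at last treatment rather than at the last scan. From C7D1 onward scans are 4 cycles apart, 4 × 28 = 112 days or 16 weeks, so last treatment can fall many weeks after the last scan. That interval is credited as progression-free although nobody looked.

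At stake is the interpretation of a secondary endpoint in a single arm of at most 24 patients. The composite response test is not affected.

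**Working it through.** **1. Is there a plan figure to reproduce?** No. The plan gives no assumed PFS median, event count or precision. Its 80.2% power concerns composite response and does not bear on this point.

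**2. What happens to a patient who stops at a first progressing scan with no second scan?**
- *Under the 7.1.4 composite:* often an event without confirmation, for example through an indication for other systemic therapy or, after the first reassessment, two or more new bone lesions. The deterioration item is less clear, because it applies where objective evidence of progression is lacking and this patient has a progressing scan.
- *Under rPFS in 2.3:* clinical progression is not an event. If the 4-week rule applies, the patient has no confirmed radiographic event and the plan is silent.
- *Under the censoring sentence:* it covers stops for other reasons, such as AE or withdrawal. It neither sends a progression stop to censoring nor excludes it from censoring.

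**3. Size if such patients are censored.** Inputs and assumptions:
- Scan grid from Section 6.1: C4D1, C7D1, C11D1, that is weeks 12, 24 and 40 (3, 6 and 10 cycles of 28 days).
- Exponential progression; deaths ignored.
- Median *m* = 13 weeks, anchored on Section 1.2, where patients on platinum therapy "experienced progression of disease with a median time of 3.0 months". This is not a figure for this regimen. *m* = 18 weeks is a second assumption.
- Unconfirmed share *u* = 20% or 35%, assumed and equal at every scan.

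The chance of progressing within an interval of *d* weeks is q = 1 − 2^(−d/m). The Kaplan-Meier factor at each scan is:
- censored at the scan (still at risk): 1 − (1−u)q
- censored just before it: 1 − (1−u)q / (1 − uq)

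*m* = 13, *d* = 12: q = 1 − 2^(−12/13) = 0.4726. Two equal intervals give week 24 as the factor squared.

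| u | Just before scan | At scan |
|---|---|---|
| 0 | 0.5274² = 27.8% | 27.8% |
| 20% | (1 − 0.3781/0.9055)² = 0.5824² = 33.9% | 0.6219² = 38.7% |
| 35% | (1 − 0.3072/0.8346)² = 0.6319² = 39.9% | 0.6928² = 48.0% |

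Every week-12 value is above 50% and every week-24 value below it, so the reported median stays at week 24. Out of 24 patients, the unconfirmed number by week 24 is u × (1 − 0.278) × 24, about 3.5 at 20% and 6.1 at 35%.

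If the loss is concentrated early (50% unconfirmed at week 12, 25% later), week-24 PFS is 41.3-49.3%, with the median again at week 24.

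*m* = 18: q = 0.3700 for 12 weeks and 0.4600 for 16 weeks.
- u = 0: week 12 is 63.0% and week 24 is 0.6300² = 39.7%, so the median is week 24.
- u = 35%: week 24 is 0.7237² = 52.4% (before) to 0.7595² = 57.7% (at). Week 40 is 0.5237 × 0.6437 = 33.7% to 0.5768 × 0.7010 = 40.4%. The median moves to week 40 under both conventions.

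**4. Size if they are counted as events on the first scan date:** u = 0, so there is no bias from this source.

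**The case against.** A reader might infer that the plan discards every progression without a second scan, so that the fastest progressors drop out and PFS is necessarily overstated. The documents do not support that.

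- Section 8.3.3 adopts Section 7.1.4, under which several non-scan events and later bone lesions count without a second scan. For a PFS defined that way, many unstable patients are already events. This stands, but it does not help rPFS, whose event in Section 2.3 is narrower.
- The censoring sentence names stops for reasons other than progression. Censoring an unconfirmed progressor is one possible reading, not written text. This stands.
- Footnote 6 requires the confirming scan without limiting it to patients on treatment, and the note to Table 7.1 asks for efforts to document progression after discontinuation. So it cannot be said that confirmation never happens. But no visit carries the scan, and nothing says what to do when it is missing.
- The confirmation text sits under Secondary Objective 4, which is PSA progression-free survival in Section 2.3. It may not have been meant for rPFS. If so, rPFS has no rule at all, which leaves the same gap.
- The unconfirmed share is assumed, and at the one median anchored in the documents the reported median does not move at 20% or 35%. This stands and limits the claim about size.
- PFS carries no hypothesis test or stopping rule, so the consequence is confined to estimation.

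**Conclusion.** The gap is real: confirmation is required, its availability depends on how the patient is doing, and the analysis of an unconfirmed progression is not stated. It is clearest for rPFS, where clinical progression is not an event. The direction of any bias is upward; whether it occurs depends on how the gap is filled. Under the assumptions above, the 24-week rate gains about 6 to 11 points at 20% unconfirmed and 12 to 20 points at 35% with a 13-week median. The median moves by one scan, from week 24 to week 40, only in the 18-week case at 35%. These figures show what is at risk and are not a forecast. The size of the death-only alternative was not calculated here.

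Separately, the instruction that patients stopping for other reasons "will be censored by the date of last treatment" is written text and credits unobserved progression-free time. The point should be corrected, but it does not threaten the primary analysis.

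**What to change.** In Section 8.3.3, under Secondary Objective 2 as well as where the text now sits:

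1. Date the event at the first scan showing radiographic progression, unless a later scan at or after the confirmation interval refutes it. Count progression with no later scan, because the patient stopped for progression, started new anticancer therapy or died, as an event on the first scan date.
2. Censor patients without an event at the last adequate tumour assessment, not at last treatment.
3. Reconcile the confirmation rules in 8.3.3, the bone-lesion text of 7.1.4 and footnote 6 of 6.1. State whether the non-scan items of the 7.1.4 composite are events for each PFS endpoint, and which endpoint the Objective 4 paragraph governs.
4. Add an rPFS sensitivity analysis that counts unequivocal clinical progression as an event.

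The cost is analysis-plan wording and a few lines of code, with no extra scans. Reported PFS may be slightly less favourable. If the sponsor already means to count these patients, item 1 changes no result and only removes a choice that could otherwise be made after the data are seen.

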### 8.3.4 Exploratory/Correlative Analysis/Assessments

Exploratory Objective 1 Analysis: To explore the association between baseline metastatic tumor characteristics including t-SCNC, AR, RB1 loss, and immune response transcriptional signatures with clinical outcomes

Exploratory Objective 2 Analysis: To evaluate objective response rate and median progression-free survival by irRECIST criteria

Exploratory Objective 3 Analysis: To evaluate the association between immune related AEs (irAEs) and clinical efficacy outcomes

Exploratory Objective 4 Analysis: To evaluate the association between baseline and change from baseline in circulating T cell and myeloid cell subsets with clinical outcomes

Exploratory Objective 5 Analysis: To explore the mechanism of skin rash in patients receiving combination of apalutamide plus cetrelimab

Exploratory Objective 6 Analysis: To explore the association between genomic and epigenomic features of circulating tumor DNA with clinical outcomes

Exploratory Objective 7 Analysis: To explore the association between circulating tumor cell (CTC) characteristics including heterogeneity, overall CTC count, and expression of markers of interest (AR, CD56, cytokeratin) with clinical outcomes

Quantification of circulating T cell subsets will be performed using mass cytometry analysis of whole blood. The percent change from baseline in the circulating T cell subsets will be reported using descriptive statistics (e.g. median, range, standard deviation). In an exploratory fashion, the study cohort will be dichotomized by those with percent change from baseline above and below median and efficacy outcomes will be compared between dichotomized subgroups using log-rank test for time-to-event endpoints (e.g. PFS, duration of response) and Fisher's exact test for categorical variables (e.g. composite response rate, objective response rate, PSA50 response rate).

Baseline metastatic tumor biopsies will be evaluated for following biomarkers of interest:

- Genomic alterations by targeted next-generation sequencing including presence of *RB1* loss
- Transcriptional profiling and application of previously validated signatures and specific genes implicated with immune response, t-SCNC, *RB1* loss, and AR activity
- Histologic assessment for t-SCNC morphology
- When feasible, immunohistochemical analysis to identify PD-L1 expression level and tumor infiltrating lymphocytes

As of Protocol Amendment 1.8 dated 07-24-2023, the italicized analyses below will no longer be performed. Epic Sciences is no longer involved in sample analysis and will return UCSF samples back to UCSF.

*Circulating tumor cells be analyzed using the Epic Sciences' platform for the following biomarkers of interest:*

- *Heterogeneity score*
- *NEPC probability using previously published prediction tool (Beltran et al. CCR 2015)*
- *Enumeration*
- *Expression of AR, CD56, cytokeratin, and RB1 using IF assays*

Circulating tumor DNA will be analyzed by the [name] laboratory at UCSF for the following biomarkers of interest:

- Genomic alterations by targeted next-generation sequencing including presence of *RB1* loss
- Inference of gene expression of target genes of interest, including AR, EZH1, ASCL1, using 5-hydroxymethyl cytosine (5-hmC) sequencing of ctDNA

The association between the above tissue-based biomarkers (baseline and change from baseline) with clinical efficacy endpoints including PFS, ORR, PSA50, and overall survival will be analyzed using log-rank test for time-to-event endpoints (e.g. PFS, duration of response) and Fisher's exact test for categorical variables (e.g. composite response rate, objective response rate, PSA50 response rate).

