Identification of t-SCNC currently relies on histologic evaluation of a metastatic tumor biopsy, which can be difficult to obtain in patients owing to the sclerotic nature of this bone-tropic disease entity. Contrary to the classic clinical characteristics of *de novo* t-SCNC, the presence of visceral metastases or elevation of serum neuroendocrine markers does not reliably identify t-SCNC on paired tumor biopsies. Several clinical and/or genomic hallmarks enrich for the identification of t-SCNC, including the presence of *RB1* genomic loss on somatic tumor profiling, as well as the presence of low PSA secretion in relation to metastatic disease burden.

Among 183 evaluable patients, low PSA secretion (PSA < 5 ng/mL) with concomitant high metastatic disease burden (> 5 metastases on conventional imaging) was found in 15 patients (8%) and was associated with enrichment for t-SCNC transcriptional signature, low AR transcriptional activity. *RB1* genomic loss is enriched in t-SCNC vs. adenocarcinoma biopsies (Aggarwal et al. JCO 2018) and is likewise associated with significant shortened survival (Chen et al. Eur Urol 2019).

[figure not shown]

Figure 1.2 AR Transcriptional Signature Score and T-SCNC Signature Score

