#### 3.3.1 Inclusion Criteria

1. Participants must have histologically confirmed prostate adenocarcinoma at the time of diagnosis, with subsequent development of metastatic castration-resistant prostate cancer. Prostate adenocarcinoma with neuroendocrine features (e.g. positive chromogranin and/or synaptophysin expression by IHC) is allowed.
2. Evidence of disease progression (PD) by PSA and/or radiographic progression by PCWG3 criteria at the time of study entry.
3. Prior progression on at least one androgen signaling inhibitor (e.g. abiraterone acetate, apalutamide, enzalutamide, darolutamide). Treatment with prior androgen signaling inhibitor may have been initiated in either the CSPC and/or CRPC setting.
4. Patients must be evaluable for the primary endpoint of composite response and must have either serum PSA > 2 ng/mL during Screening and/or measurable disease by RECIST 1.1 criteria.

5. Participants must have clinicogenomic evidence of treatment emergent small cell neuroendocrine prostate cancer as defined by one or more of the following:
  - i. Histologic evidence of small cell neuroendocrine prostate cancer on evaluation of CRPC tissue by centralized pathology review  
and/or
  - ii. Presence of loss-of-function mutation or deletion of *RB1* on a CLIA-approved genomic-sequencing platform. Either monoallelic or biallelic mutations in *RB1* are allowed.
6. No more than one prior line of taxane-based chemotherapy administered in the mCRPC setting. Chemotherapy administered in the castration-sensitive setting does not count towards this limit. Prior carboplatin is allowed and does not count as an additional line of therapy when given in conjunction with taxane.
7. Castrate level of serum testosterone at study entry (<50 ng/dL). Patients without prior bilateral orchiectomy are required to remain on LHRH analogue treatment for duration of study.
8. No other systemic anti-cancer therapies administered other than LHRH analogue within 14 days or, 5 half-lives, whichever is shorter, prior to initiation of study treatment. AEs related to prior anti-cancer treatment must have recovered to Grade  $\leq 1$  with the exception of any grade alopecia and Grade  $\leq 2$  neuropathy.
  - b. Patients receiving apalutamide prior to study entry may continue treatment at their current apalutamide dose level without requirement for wash-out period.
9. Age  $\geq 18$  years

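### Small cell histology and RB1 loss are alternative entry routes, so the unadjusted comparison of either marker with outcome in section 8.3.4 can be biased or reversed in sign

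*Combined protocol and SAP*

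**What the plan says.** Section 3.3.1, criterion 5: "Participants must have clinicogenomic evidence of treatment emergent small cell neuroendocrine prostate cancer as defined by one or more of the following". Two routes follow, joined by and/or. The first is "Histologic evidence of small cell neuroendocrine prostate cancer on evaluation of CRPC tissue by centralized pathology review". The second is "Presence of loss-of-function mutation or deletion of *RB1* on a CLIA-approved genomic-sequencing platform", with the note that "Either monoallelic or biallelic mutations in *RB1* are allowed".

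Exploratory Objective 1 in section 8.3.4 reads "To explore the association between baseline metastatic tumor characteristics including t-SCNC, AR, RB1 loss, and immune response transcriptional signatures with clinical outcomes". Section 8.3.4 uses the same two features as baseline biomarkers. Its list for the metastatic biopsy includes RB1 loss by targeted sequencing and "Histologic assessment for t-SCNC morphology"; RB1 loss appears again under circulating tumor DNA. The section then says that "The association between the above tissue-based biomarkers (baseline and change from baseline) with clinical efficacy endpoints" (PFS, ORR, PSA50 and OS are named) will be analyzed by log-rank and Fisher's exact tests. Section 2.4 gives composite response and PFS as the endpoints for Exploratory Objective 1.

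No stratified or joint analysis is named, and nothing is said about the entry rule. That each marker is tested separately is an inference from the tests named; the text does not say so outright.

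Section 1.2 says of RB1 that "genomic loss is enriched in t-SCNC vs. adenocarcinoma biopsies", without giving a size.

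**The concern.** The entry rule empties one cell of the histology-by-RB1 table: patients with neither feature cannot enrol. A comparison of RB1 loss with RB1 intact then sets a mixture (both features, or RB1 only) against patients who are all histology-positive. A comparison by histology sets a mixture against patients who are all RB1-altered. Each contrast carries part of the other marker's effect.

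The protocol gives reasons to expect some effect. Section 1.2 reports poorer prognosis and lower AR signaling in t-SCNC, and shorter survival with RB1 loss. Section 1.4 suggests that t-SCNC may respond better to anti-PD-1 therapy. At stake is a biomarker statement that credits RB1 with a difference due to histology, or the reverse, on a question the trial set out to explore.

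**Working it through.** **The plan's own figures.** Section 8.1.1 gives the only computed design: stop at 2 or fewer responses in 14, reject at 8 or more in 24. Exact power at 40% is the sum over x = 3 to 14 of P(X1 = x; 14, 0.40) × P(X2 ≥ 8 - x; 10, 0.40) = 0.8024, which agrees with the stated 80.2%. The exact type I error at 15% is 0.0194, within the stated 0.025. The plan gives no figure for the RB1 or histology analysis.

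**The enrolled cells.** Let H be small cell histology and R an RB1 alteration, both by eligibility status. The enrolled cells are H+R+, H+R- and H-R+.

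**RB1 comparison when RB1 has no effect.** Let p+ and p- be response with and without the histology, d = p+ - p-, and q = P(H+ | R+, enrolled).

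- RB1-intact group: all H+, so response is p+.
- RB1-altered group: q·p+ + (1-q)·p-.
- Difference, altered minus intact: -(1-q)d.

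The same identity holds for the proportion progression-free at any fixed time.

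**Histology comparison when only RB1 acts.** With RB1 effect e and s = P(R+ | H+), the H+ minus H- difference is -(1-s)e.

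**Size.** The documents give none of q, d, s or e. For an assumed d = +0.25 (40% vs 15%):

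| q | RB1 difference with no RB1 effect |
|---|---|
| 0 | -0.25 |
| 0.25 | -0.19 |
| 0.50 | -0.125 |
| 0.75 | -0.06 |
| 1 | 0 |

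With d = -0.25 every sign reverses. With d = 0 every entry is 0.

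**Illustration of a sign reversal.** Take histologic t-SCNC at 17% (section 1.2) and assume RB1 alteration in 50% of H+ and 10% of H-.

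- H+R+ = 0.17 × 0.5 = 0.085; H+R- = 0.085; H-R+ = 0.83 × 0.1 = 0.083.
- q = 0.085 / 0.168 = 0.51.
- Enrolled RB1 difference at d = +0.25: -(1 - 0.506) × 0.25 = -0.124.
- Unselected population: P(H+ | R+) = 0.506 and P(H+ | R-) = 0.085 / 0.832 = 0.102, so the difference is (0.506 - 0.102) × 0.25 = +0.101.

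**Chance of a falsely significant result.** Two-sided Fisher at an assumed 0.05, with 12 RB1-altered and 12 intact patients, rejects 1.7% of the time when response is 30% in both groups. At d = +0.25 it rejects 14.7%, 8.1% and 4.4% of the time for q = 0, 0.25 and 0.5. The main risk is therefore a misleading point estimate, more than a significant p-value.

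**After restriction.** Comparing RB1 only within H+ removes the term in d. At an assumed split of 8/8/8, Fisher rejects 1.9% of the time when both groups respond at 40%, and has 6.9% power for 40% vs 15%.

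**The case against.** The strongest case on the other side has four parts.

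- **The bias is conditional.** A reader might infer that the entry rule must produce a false RB1 or t-SCNC effect. The documents do not support that: the bias vanishes if the other marker does not affect outcome, or if the group being compared is not a mixture. A reader might also infer that RB1 loss would look favourable, or attach an odds ratio to it. Both depend on an assumed response gap. With RB1 alteration in 40% of H+ and 10% of H-, q = 0.068 / 0.151 = 0.45. Response of 10% in H+ and 40% in H- gives 26.5% vs 10% (odds ratio 3.24); swapping the rates gives 23.5% vs 40% (odds ratio 0.46). Sections 1.2 and 1.4 point in opposite directions, so neither sign can be preferred.
- **The RB1-only group may be small.** Section 8.1.2 expects about 15% of mCRPC patients to meet the whole t-SCNC definition, whereas the 50%/10% illustration implies 0.17 + 0.083 = 25.3%. The 15% and 17% may have different denominators, so they do not show that the group is empty, but they suggest a larger q. With RB1 alteration in an assumed 2% of H-, q = 0.085 / (0.085 + 0.0166) = 0.84 and the difference shrinks to -0.04.
- **The empty cell is exact only for eligibility status.** Analyzed calls come from a baseline biopsy or ctDNA, which need not be the qualifying specimen or assay. The biopsy may be waived (criterion 14) and is largely optional (section 6.4.1). Criterion 5 does not require both markers to be assessed. Where t-SCNC means a transcriptional signature, the constraint is only indirect.
- **The consequence is small.** This is one exploratory objective, with no decision attached to it.

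All four stand as limits on size and certainty. None supplies a safeguard: the plan still relates two alternative entry criteria to outcome by unadjusted tests, without comment.

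**Conclusion.** The point holds as a limited one. By eligibility status no enrolled patient lacks both markers. If either marker affects outcome, the marginal comparison for the other can be biased or reversed in sign, by -(1-q)d for RB1 and -(1-s)e for histology. At an assumed effect of 25 percentage points the bias runs from 0 to 25 points in either direction, depending on overlap that the documents do not report. It applies strictly to the histology and RB1 sequencing items, not to the transcriptional signatures. The primary analysis and N = 24 are unaffected.

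**What to change.** In section 8.3.4:

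1. Report response and PFS descriptively, with confidence intervals, for three groups: histology only, RB1 only, and both.
2. Keep not tested or not assessed as a separate category, never counted as RB1-intact or histology-negative.
3. Make any RB1 comparison only within histology-positive patients (both vs histology only), and any histology comparison only within RB1-altered patients (both vs RB1 only).
4. State that marginal comparisons of these two markers are not interpretable under the entry rule.

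This adds no patients or procedures, but patients assessed for only one marker will fall outside the three groups. The groups are smaller and power is very low (about 7% for 40% vs 15% at the assumed 8/8/8 split), so the results can only be descriptive. Whether the RB1 effect differs by histology cannot be estimated at all, because the cell with neither feature is empty.
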